7.2.3 Consumption of BAX326

Summary statistics will be provided for the product consumption of BAX326 by treatment regimen:

- Number of infusions per month and per year
- Weight-adjusted consumption per month and per year
- Weight-adjusted consumption per bleeding event

8. SAFETY EVALUATION

The analysis of safety endpoints will be performed on the FAS.

Regarding missing data in AE records:

- Handling of unknown causality assessment:
 - If a subject experiences an AE with a missing causality assessment, the relationship of the AE will be counted as “related”.
- Handling of unknown severity grades:
 - If a subject experiences more than one AE categorized under the same preferred term, one of them is categorized as “severe” and one of them is categorized as “unknown”, the severity of this AE should be counted as “severe”.
 - If a subject experiences more than one AE categorized under the same preferred term, one of them is categorized as “mild” or “moderate” and one of them is categorized as “unknown”, the severity of this AE should be counted as “unknown”. A column “UNK” should be inserted for those AEs at the end of the table (before the “Total” column if applicable).

8.1 Analysis of Primary Safety Outcome Measure

The number of possibly or probably related adverse events that occurred during or after first BAX326 infusion will be summarized. In addition, the number of subjects with possibly or probably related adverse events that occurred during or after first BAX326 infusion will be also summarized.

8.1.1 Adverse Events

AEs that occurred during or after first IP infusion will be presented in summary tables. Summary tables shall indicate the number of subjects who experienced adverse events. Separate tables will be carried out for temporally associated adverse events; and for temporally associated or causally related adverse events.

In addition, tables will be prepared to list each AE, the number of subjects who experienced an AE at least once, and the rate of subjects with AE(s). AEs will be grouped by system organ class. Each event will then be divided into defined severity grades (mild, moderate, severe). The tables will also divide the AEs into those considered related (a “possibly related” or a “probably related” AE will be considered as a “related AE”) to the treatment and those considered unrelated (an “unlikely related” or a “not related” AE will

be considered as an “unrelated” AE). These tables will also be carried out for temporally associated adverse events; and for temporally associated or causally related adverse events.

All AEs; temporally associated AEs; causally related AEs; and temporally associated or causally related AEs will also be summarized by system organ class, preferred term, including the number of AEs, the number (%) of unique subjects, the frequency category (very common: $\geq 10\%$, common: $\geq 1\%$ to $< 10\%$, uncommon: $\geq 0.1\%$ to $< 1\%$, rare: $\geq 0.01\%$ to $< 0.1\%$, very rare: $< 0.01\%$) and the number of IP-infusions associated with an AE.

Temporally associated AEs are defined as AEs that begin during infusion or within 24 hours (or 1 day where time of onset is not available) after completion of infusion, irrespective of being related or not related to treatment.

AEs and SAEs for each subject, including the same event on several occasions, will be listed separately, giving both MedDRA preferred term and the original term used by the investigator, system organ class, severity grade, seriousness, relation to the treatment, onset date, and stop date.

AEs that occurred before first IP infusion will be listed separately.

8.2 Analysis of Secondary Safety Outcome Measures

A table will present the number (%) of subjects for the following safety endpoints: occurrence of inhibitory and (treatment emergent) total binding antibodies to FIX, occurrence of (treatment emergent) antibodies to CHO proteins and rFurin, occurrence of severe allergic reactions (e.g. anaphylaxis), and occurrence of thrombotic events.

As mentioned in section 12.7.1 of the protocol, indeterminate results of total binding antibodies to FIX, antibodies to CHO proteins or rFurin will be set to negative. Occurrence of treatment emergent total binding antibodies to FIX, antibodies to CHO proteins and rFurin is defined by more than 2-dilution increase as compared to levels at screening visit (e.g. negative to 1:80).

8.2.1 Hematology and Clinical Chemistry Laboratory Evaluations

For each hematology and clinical chemistry laboratory assay, shift tables will display two way frequencies for the number of abnormal/normal values from the screening, compared to the assessment at end of study. For abnormal values, frequencies will be split up by clinical significance. All abnormal hematology and clinical chemistry result will be listed, giving units of measurement and clinical relevance of result provided by investigators.

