Subsequent study visits will be performed every 3 monthsxiii  $\pm 1$  week after study start (ie, screening visit) until study completion; additional visits may occur if clinically indicated. Hemostatic efficacy and the occurrence of AEs will be evaluated based on the review of the patient diary. Testing for IR, inhibitory and binding antibodies, clinical chemistry and hematology will be performed at the same time points. In addition to the time points mentioned above, the presence of inhibitory and total binding antibodies to FIX will be tested whenever clinically indicated, e.g. on lack of response to treatment, or if severe allergic reactions occur, such as anaphylaxis.

At the same time points health resource use will also be determined. Every other visit (ie, every 6 months  $\pm 1$  week), data on HR QoL will be collected.

For the hemostatic efficacy assessment the following information will be recorded by the subject or subject's legal representative or by authorized study site personnel in the patient diary: bleeding location, type, severity, onset date and time, infusion date and time, analgesics required, and clinical efficacy according to the rating scale.

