#### **8.2 Duration of Study Period(s) and Subject Participation**

The total period of study participation per study subject will vary and can be up to a maximum of 68 months, depending on the date of subject enrollment and the product licensure in the subject's respective country, and whether the subject has accumulated a total of 100 EDs to BAX326 during the course of the Pivotal (# 250901) or Pediatric (# 251101) Study and the Continuation Study (# 251001), whichever occurs last, but will not last beyond December 31, 2016.

For newly recruited subjects, the study participation will be up to approximately 100 EDs, but not beyond December 31, 2016. However, a limited number of patients may not have reached 100 EDs by that date and they will continue until they have reached approximately 100 EDs.

Subjects will participate in this continuation study until BAX326 is licensed in their respective countries, and they have accumulated a total of at least 100 EDs to BAX326, however, no later than December 31, 2016.

The duration of the study will be approximately 68 months depending on the date of licensure in subjects' countries.

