#### **14.3.2.3 Safety**

Frequency counts and percentages will be calculated for the following variables: occurrence of inhibitory antibodies to FIX, occurrence of total binding antibodies to FIX, occurrence of antibodies to CHO proteins and rFurin, occurrence of severe allergic reactions (e.g. anaphylaxis), and occurrence of thrombotic events.

Analysis of AEs that occurred during or after treatment application will be descriptive. Serious and non-serious AEs will be cross-tabulated for severity and relation to the treatment, giving the number of AEs and the number (proportion) of unique subjects who experienced adverse events. All AEs will be categorized according to the MedDRA dictionary and summarized by system organ class and preferred term.

Clinically significant changes in laboratory parameters and vital signs will be reported.

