2.6 Sample Size and Power Calculations

The sample size is not based on statistical consideration and is determined by the number of subjects of the BAX326 pivotal protocol 250901 and the pediatric protocol 251101, who are willing to participate in this study and meet the eligibility criteria as well as regulatory requirements.

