3.2.2 Safety and Immungenicity

- Development of inhibitory and total binding antibodies to FIX
- Development of antibodies to CHO proteins and rFurin
- Occurrence of severe allergic reactions, e.g. anaphylaxis
- Occurrence of thrombotic events
- Clinically significant changes in routine laboratory parameters (hematology and clinical chemistry), and vital signs

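### Laboratory safety is tabulated only at screening and end of study, so no table counts subjects with a new clinically significant abnormality at any time on study

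*SAP*

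**What the plan says.** SAP 3.2.2 names as a secondary safety outcome: "Clinically significant changes in routine laboratory parameters (hematology and clinical chemistry), and vital signs". Protocol 14.3.2.3 commits to it in one line, without a format: "Clinically significant changes in laboratory parameters and vital signs will be reported".

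On collection, Protocol 8.1.1 says "Subsequent study visits will be performed every 3 months" and adds "Testing for IR, inhibitory and binding antibodies, clinical chemistry and hematology will be performed at the same time points". Protocol 12.7.3 gives newly recruited subjects a Week 4 test as well, and tests everyone at termination and when clinically indicated. Participation "can be up to a maximum of 68 months" (Protocol 8.2).

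On analysis, SAP 8.2.1 plans for each assay that "shift tables will display two way frequencies for the number of abnormal/normal values from the screening, compared to the assessment at end of study", and adds: "For abnormal values, frequencies will be split up by clinical significance". It also lists all abnormal results with the investigator's view of clinical relevance. SAP 5.2 item 3 keeps unscheduled and repeat measurements out of the descriptive statistics and puts them in listings.

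**The concern.** The outcome concerns change over the whole treatment period, but the laboratory table looks at one post-screening moment. A clinically significant value that appears mid-study and has resolved by the last visit does not enter it. A value drawn at an unscheduled visit, often because something looked wrong, does not enter it either.

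What is at stake is a plain answer to a question in the first study objective: how many subjects developed a clinically significant change in a given parameter while on BAX326? As planned, a reader would have to count this by hand from a listing that covers up to about 23 scheduled visits per subject.

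**Working it through.** **1. Is there a figure to reproduce?** No. The study is descriptive ("The sample size is not based on statistical consideration", SAP 2.6), and no event rate is stated for this outcome. The check is a count of assessments and a reading of which output each value reaches.

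**2. Assessments against tabulated points.** The protocol counts a month as 30 days, so 3-monthly visits = floor(days / 90).

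- 68-month maximum: 68 × 30 = 2,040 days; 2,040 / 90 = 22.7, so 22 visits. Adding termination gives about 23 post-screening assessments. One is in the shift table; 22/23 = 96% are outside it.
- Newly recruited subject, 100 exposure days at two per week: 50 weeks = 350 days; 350 / 90 = 3.9, so 3 visits. Adding Week 4 and termination gives about 5. One is in the shift table; 4/5 = 80% are outside it.

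**3. Where a clinically significant value goes** (Protocol 12.7.6.1; SAP 5.2, 8.1.1, 8.2, 8.2.1).

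| Value | Output |
|---|---|
| Present at screening or end of study | Shift table, split by clinical significance; listing |
| Interim or unscheduled, judged a new AE | AE tables, with number (%) of subjects by preferred term; listing |
| Interim, judged not a new AE | Listing only |
| Unscheduled, judged not a new AE | Listing only |

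The investigator decides on clinical significance first and on AE status second. Recorded reasons for a clinically significant value not being an AE are laboratory error, preexisting disease, a symptom of an AE already recorded, or another specified issue.

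**4. Comparison with the other secondary safety outcomes.** SAP 3.2.2 lists five. The table in SAP 8.2 gives number (%) of subjects for four: FIX antibodies, antibodies to CHO proteins and rFurin, severe allergic reactions, and thrombotic events. The laboratory part of the fifth gets the shift table and listing only.

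**5. Illustration of the difference between ever affected and affected at the end.** Let p be the chance of a clinically significant value at any one assessment. The documents do not give p; the values below are assumed, as is independence between visits. Ever affected = 1 − (1 − p)^K.

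| Assumed p (= end-of-study figure) | Ever affected, K = 5 | Ever affected, K = 23 |
|---|---|---|
| 0.5% | 2.5% | 10.9% |
| 1% | 4.9% | 20.6% |
| 2% | 9.6% | 37.2% |

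For example, 1 − 0.99^23 = 20.6%. If abnormalities persist or cluster within subjects, the gap is smaller.

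**The case against.** The strongest reply is that the outcome is already reported. The shift table counts, per assay, moves to a clinically significant abnormal value at the last visit. The AE definition in Protocol 12.1.1 includes an abnormal laboratory finding, so a new and clinically significant change would ordinarily become an AE and be counted, however brief. Of the reasons for not recording an AE, laboratory error and preexisting disease are mostly not new treatment-period changes, and a symptom of a recorded AE is already counted under that AE. Protocol 14.3.2.3 reserves counts and percentages for the other safety variables and prescribes no format here, so the SAP does not depart from the protocol.

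Most of this stands, and it rules out three stronger readings that a reader might infer:

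- *That the outcome has no frequency figure, or that transient changes reach no table.* The shift table gives an end-of-study prevalence, and transient changes judged to be AEs are in the AE tables.
- *That 80–96% of laboratory events are lost to the analysis.* Those are shares of scheduled assessments outside the shift table. They become shares of abnormalities only if each lasts one visit and is equally likely at any visit, and even then they ignore capture as AEs.
- *That subjects discontinued for raised liver enzymes drop out of the shift table.* Protocol 10.6 asks for every effort to complete a termination visit, which includes these tests. A missing sample is possible but not implied.

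What the reply does not remove is that the outcome is defined by clinical significance, not by AE status. AE tables are organised by diagnosis or preferred term (Protocol 12.1.2 prefers a diagnosis), so they do not give a count per laboratory parameter. A worsening attributed to preexisting disease, or set aside for another reason, can be flagged clinically significant and still appear only in the listing.

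**Conclusion.** The point holds as a reporting gap in a descriptive secondary outcome. The plan has no table, by parameter, of the number (%) of subjects with a new clinically significant abnormality at any time on study. The laboratory table uses 1 of about 5 to 23 scheduled post-screening assessments, depending on follow-up. Interim and unscheduled clinically significant values that are not recorded as AEs are visible only in listings.

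The visit counts assume the scheduled visits are kept and that termination is separate from the last 3-monthly visit. How many subjects are affected cannot be derived from the documents: it depends on an unstated per-visit risk and on how often investigators record such values as AEs. The primary outcome, AEs possibly or probably related to the product, is unaffected. The change should be made, but it is modest.

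**What to change.** In SAP 8.2.1, add for each hematology and chemistry parameter:

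1. the number (%) of subjects with at least one new post-screening value that the investigator flagged as clinically significant, with new defined relative to screening;
2. a shift from screening to the worst post-screening value, with low and high directions shown separately for two-sided parameters such as sodium, potassium and glucose.

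Amend SAP 5.2 item 3 so that unscheduled and repeat values count in these two tables; otherwise the new tables would contradict it. Show results by cohort or per subject-year (SAP 10.2 already uses subject-years for health resource use), because SAP section 5 pools cohorts with very different follow-up. Keep the end-of-study shift as a supplement.

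No new data are needed, since the investigator's judgement on each abnormal value is already on the eCRF. The cost is programming: about 25 parameters (12 hematology, 13 chemistry), repeated for the age groupings in SAP section 5. The downside is that crude ever-affected percentages rise with follow-up: at the same assumed 1% per-visit risk they are 4.9% over 5 assessments and 20.6% over 23. They should not be read without the exposure alongside.

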8.2.2 Vital Signs

A summary table of changes in vital signs (pulse rate, systolic/diastolic blood pressure, respiratory rate, body temperature) from pre-infusion to end of study will be provided.

The percent change in vital signs will be calculated as:

$$((\text{vital_sign2}-\text{vital_sign1})/\text{vital_sign1})*100;$$

where `vital_sign1` denotes the vital sign value at the pre-infusion time-point and `vital_sign2` denotes the end of study vital sign value.

8.3 Extent of Exposure

A summary table of BAX326 exposure days (EDs) will be created by treatment regimen as well as for all treatment regimens together. Exposure days (after study entry of the Continuation study) during the surgery study (251002) should be taken into account.

8.4 Viral Serology

Each viral marker test will be summarized using a shift table between the screening and the termination visits. Any changes from the assessment at the screening visit will also be listed.

9. EVALUATION OF PHARMACOKINETICS

All PK analyses will use the actual sampling times, not nominal times specified in the protocol, wherever possible. Actual sampling times will be defined as time from the start of infusion to the blood sample collection time. A deviation from the protocol-specified drawing time window will not be a reason to exclude an observation. Samples with unknown actual and planned collection date/time and/or where the concentration could not be determined, or where results were biological implausible will be eliminated before the calculations.

The pediatric (< 12 years) and the adolescent/adult (\geq 12 years) data will be summarized separately.

Regarding missing values / values below the lower limit of quantification (LLOQ):

- FIX activity level:
 - If pre-infusion / post-infusion value is missing then no imputation will be done.
 - If pre-infusion value reported as < 1% (i.e. LLOQ):
 - For calculation of IR over time, use 0.5%.
 - For descriptive statistics, use 0.5%.
 - For calculation of PK parameters, use 0%.
 - If post-infusion value reported as < 1% (i.e. LLOQ):
 - For descriptive statistics, use 0.5%.
 - For calculation of PK parameters, remove value from the calculation of PK parameters.
- Time:
 - Missing start time of infusion:
 - If stop time and actual collection time are available, then stop time of infusion will be taken for further calculation (i.e. time difference between actual end date/time of infusion and date/time blood sample drawn).
 - If stop time and/or actual collection time is not available and planned collection date/time is available, then use planned collection date/time.
 - Otherwise, this PK sample will be taken out from the PK analysis.
 - Missing actual collection date/time:
 - If planned collection date/time is available, then use planned collection date/time.
 - Otherwise, this PK sample will be taken out from the PK analysis.

9.1 IR Over Time

Analysis of IR over time will be carried out on the FAS.

IR_{30min} in IU/dL/IU/kg will be calculated as:

$$\text{IR}_{30\text{min}} = \frac{C_{30\text{min}}[\text{IU/dL}] - C_{\text{pre-infusion}}[\text{IU/dL}]}{\text{dose per kg body weight [IU/kg]}}$$

where C_{30min} and C_{pre-infusion} relate to the unadjusted concentration values.

IR_{30min} of FIX will be summarized for baseline and end of study using descriptive statistics. Also the change from baseline to end of study will be described using summary statistics.

These tables will be created for the on-demand treatment only (i.e. subjects who received on-demand treatment exclusively over the whole study period), for the overall prophylaxis (combined standard, modified and PK-tailored prophylaxis) only, for subjects who received on-demand treatment and any prophylaxis treatment (i.e. subjects who switched during the study) as well as for all treatment regimens together.

In addition, IR_{30min} of FIX will be provided in a by-subject listing.

The maximum allowable dose is 120 IU/kg – all cases with a dosage higher than 120 IU/kg will be excluded from the IR tables and will be only displayed in a listing.

9.2 PK Parameters from Abbreviated PK Study

Analysis of PK parameters will be performed on the PKFAS.

To ensure that FIX levels at pre-infusion are not affecting the estimation of PK parameters, post-infusion concentration data will be adjusted proportionally as follows:

$$FIX_{\text{Adjusted},t} = \left(1 - \frac{FIX_{\text{Measures,pre-infusion}}}{C_{\text{max}}}\right) * FIX_{\text{Measured},t}$$

Area under the plasma concentration/time curve from time 0 to 72 hours (AUC_{0-72h}) in IU·hr/dL will be computed using the linear trapezoidal method. The concentration at 72 hours will be interpolated from the two nearest sampling time points or extrapolated using the last quantifiable concentration and the terminal rate constant λ_z. λ_z will be estimated from the

slope of natural log-linear fitting to latter quantifiable concentrations, with largest adjusted R^2 .

Area under the plasma concentration/time curve from time 0 to infinity ($AUC_{0-\infty}$) in IU·hr/dL will be defined as $AUC_{0-t} + Ct/\lambda_z$, where t is the time of last quantifiable concentration, Ct is the last quantifiable concentration.

Elimination phase half-life ($T_{1/2}$) in hours will be calculated as

$$T_{1/2} = \log_e(2)/\lambda_z$$

where the elimination rate constant (λ_z) will be obtained by \log_e -linear fitting using least squares deviations to at least the last 3 quantifiable concentrations above pre-infusion level.

The **Mean Residence Time** (MRT) in hours will be calculated as total area under the moment curve divided by the total area under the curve:

$$MRT = \frac{AUMC_{0-\infty}[h^2 * IU/dL]}{AUC_{0-\infty}[h * IU/dL]} - TI/2$$

where $AUMC_{0-\infty}$ will be determined in a similar manner as $AUC_{0-\infty}$ and TI represents infusion duration [hr].

Systemic clearance (CL) in dL/kg/hours will be calculated as the dose in IU/kg divided by the total AUC:

$$CL = \frac{Dose[IU/kg]}{AUC_{0-\infty}[h * IU/dL]}$$

Apparent **steady state volume of distribution** (V_{ss}) in dL/kg will be calculated as:

$$V_{ss} = \frac{Dose[IU/kg] \times AUMC_{0-\infty}[h^2 * IU/dL]}{AUC_{0-\infty}^2[h^2 * IU^2/dL^2]} = CL * MRT$$

The **maximum concentration**, C_{max} , will be calculated as the maximum concentration post-infusion.

The **time to reach the maximum concentration**, T_{max} , in hours was defined as the time to reach C_{max} .

$AUC_{0-\infty}$, $AUC_{0-\infty}/Dose$, $AUC_{0-72h}/Dose$, $T_{1/2}$ (elimination phase half-life), MRT (mean residence time), CL (clearance), V_{ss} (volume of distribution at a steady state), C_{max} (maximum concentration), T_{max} (time to reach the maximum concentration) and IR (incremental recovery), will be summarized using descriptive statistics. Additionally, IR of FIX will be displayed graphically over time for each subject.

In addition, by-subject plots of FIX level against time will be presented on the linear and semi-logarithmic scales.

PK parameters will be derived using non-compartmental methods in WinNonlin® Version 6.2, or higher. Detailed specifications around the PK calculation is described in a separate document that was generated for the dosing recommendations.

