#### **6.4.1 Phase 1/3 Pivotal Study (250901)**

In the pivotal studyv, hemostatic efficacy, pharmacokinetics, safety, and immunogenicity were evaluated in a total of 73 male PTPs aged 12 to 59 years with severe or moderately severe hemophilia B. Subjects with a history of or a detectable FIX inhibitor  $\geq 0.6$  BU, a history of severe allergic reactions following exposure to FIX, evidence of severe chronic liver disease (INR  $> 1.4$ ), impaired renal function, a CD4 count  $< 200$  cells/mm^3 or any hemostatic defect other than hemophilia B were excluded from participation. The majority of subjects (88%) had arthropathy at screening and target joints (66%).

---

v Full clinical study report finalized on 11 September 2012.

In the randomized, controlled, cross-over PK portion of the study with 28 subjects, PK equivalence of BAX326 and BeneFIX was confirmed, with a 90% CI of 103% to 109% for  $AUC_{0-72\text{ h}}/\text{dose}$  (and also for  $AUC_{0-72\text{ h}}$ ) in both the PK Per Protocol Analysis Set (PKPPAS) and the PK Full Analysis Set (PKFAS). The median IR at  $C_{\max}$  was 0.88 with a range of 0.53-1.35, the mean was  $0.87 \pm 0.22$ . The median half-life was 24.58 hours with a range from 15.83 to 52.34 hours and a mean of  $26.70 \pm 52.34$ . The PK parameters remained constant at the repeat PK evaluation performed after 6 months of treatment.

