2.3 Study Population

Previously treated patients (PTPs) with severe (FIX level $< 1\%$) or moderately severe (FIX level 1-2%) hemophilia B, who completed Pivotal Study 250901 or Pediatric Study 251101, and were between 12 and 65 years of age at the time of screening for Study 250901 or < 12 years old at the time of screening for Study 251101, will be recruited in this study (Cohort 1 patients).

In addition, at least 25 BAX326 naïve subjects with severe (FIX level $< 1\%$) or moderately severe (FIX level 1-2%) hemophilia B will be newly enrolled to ensure the evaluation of long-term safety and efficacy in approximately 100 PTPs (Cohort 2 patients).

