2.4.2 Newly Recruited Subjects (Cohort 2)

Newly recruited subjects who meet **ALL** of the following criteria are eligible for this study:

1. Subject and/or legal representative has/have provided signed informed consent.
2. Subject is 2 to 70 years old at the time of screening.
3. Subject is naïve to BAX326.
4. Subject has severe (FIX level $< 1\%$) or moderately severe (FIX level 1-2%) hemophilia B (based on the one stage activated partial thromboplastin time (aPTT) assay), as tested at screening at the central laboratory.
5. Subject aged ≥ 6 years has been previously treated with plasma-derived and/or recombinant FIX concentrate(s) for a minimum of 150 EDs.
6. Subject aged < 6 years has been previously treated with plasma-derived and/or recombinant FIX concentrate(s) for a minimum of 50 EDs.
7. Subject has no evidence of a history of FIX inhibitors.
8. Subject is immunocompetent as evidenced by a CD4 count ≥ 200 cells/ mm^3 at screening.

9. Subject is HIV negative or is HIV+ with a viral load < 200 particles/ μ L ~ < 400,000 copies/mL.
10. If female of childbearing potential, subject presents with a negative pregnancy test and agrees to employ adequate birth control measures for the duration of the study.
11. Subject is willing and able to comply with the requirements of the protocol.

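### SAP 9.2's proportional pre-infusion correction cannot change T1/2 or MRT, so constant endogenous FIX of 1-2% stays in the PK results (minor; reach unknown and possibly nil)

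*SAP*

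**What the plan says.** SAP 9.2 adjusts the abbreviated-PK data before NCA: "To ensure that FIX levels at pre-infusion are not affecting the estimation of PK parameters, post-infusion concentration data will be adjusted proportionally". The formula is adjusted(t) = (1 - pre/Cmax) x measured(t), with a single multiplier for all samples of a subject.

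The terminal slope is described twice in SAP 9.2. It is first the "slope of natural log-linear fitting to latter quantifiable concentrations" with the largest adjusted R-squared. In the half-life definition it is a log-linear fit "to at least the last 3 quantifiable concentrations above pre-infusion level".

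For a pre-infusion value reported below 1%, SAP 9 has the rule "For calculation of PK parameters, use 0" (per cent), so the multiplier is then 1.

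SAP 2.3 includes subjects with "moderately severe (FIX level 1-2%) hemophilia B". For Cohort 2 the level is the one "as tested at screening at the central laboratory" (SAP 2.4.2).

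For IR over time, SAP 9.1 instead subtracts the pre-infusion value. SAP 9.2 does not say whether a pre-infusion value is residual drug or the subject's own FIX. It refers to a separate document for detailed PK specifications.

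**The concern.** A measurable pre-infusion FIX value can be the tail of an earlier dose, which keeps falling at the drug's own rate, or endogenous FIX, which stays roughly constant over 72 h. A proportional correction suits the first. The second flattens the late part of the curve, and a constant multiplier cannot undo that.

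The stated purpose of the adjustment is therefore not met for subjects with FIX of 1-2%. T1/2, MRT, AUC, CL and Vss are named secondary outcomes (SAP 3.2.3), and all five would carry the effect. Under SAP 5.5, NCA replaces the model planned in the protocol, so SAP 9.2 is now the place where baseline handling has to be right. IR over time is not affected, because it is computed by subtraction.

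**Working it through.** The plan gives no figure for remaining bias, so there is nothing of its own to reproduce.

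**Algebra.** Let a = 1 - pre/Cmax. Then log(a x C) = log a + log C, so the log-linear slope does not depend on a. In AUMC/AUC, a cancels. T1/2 and MRT are therefore identical with and without the adjustment, whatever the source of the pre-infusion value. AUC is scaled by a, and CL by 1/a.

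**Inputs.** Dose 75 IU/kg and samples at 0.5, 9, 24, 48 and 72 h (Protocol Table 11.1-2). Mean IR 0.87; the median "was 0.88 with a range of 0.53-1.35" (Protocol 6.4.1). "The median half-life was 24.58 hours with a range from 15.83 to 52.34 hours" (same section). Endogenous FIX 1 or 2 IU/dL. Assumptions: one-phase decay, no assay error, time-zero value back-extrapolated.

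**Model.** C(t) = 75 x 0.87 x 2^(-t/24.58) + endogenous.

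| Time (h) | Drug only | Drug + 1 | SAP-adjusted (a = 1 - 1/65.34 = 0.9847) |
|---|---|---|---|
| 0.5 | 64.34 | 65.34 | 64.34 |
| 9 | 50.62 | 51.62 | 50.83 |
| 24 | 33.16 | 34.16 | 33.64 |
| 48 | 16.85 | 17.85 | 17.58 |
| 72 | 8.57 | 9.57 | 9.42 |

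**T1/2, last three points.** These are equally spaced, so lambda_z = ln(C24/C72)/48.
- Drug only: ln(33.16/8.57)/48 = 0.02820, T1/2 24.58 h.
- Endogenous 1%: ln(34.16/9.57)/48 = 0.02652 unadjusted, and the same from 33.64/9.42. T1/2 26.14 h, +6.3%.
- Endogenous 2%: ln(35.16/10.57)/48 = 0.02505, T1/2 27.67 h, +12.6%.

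**T1/2, best adjusted R-squared** (selects all five points). 1%: lambda_z 0.02690, T1/2 25.77 h, +4.8%. 2%: lambda_z 0.02574, T1/2 26.93 h, +9.6%.

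**Other parameters** (shift against the same NCA on the drug-only curve, which gives AUC 2358, MRT 34.1 h and Vss 1.085; best adjusted R-squared, last three points in brackets):

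| | 1% | 2% |
|---|---|---|
| AUC | +3.6% (+3.9%) | +7.3% (+7.8%) |
| CL | -3.5% (-3.7%) | -6.8% (-7.2%) |
| MRT | +5.4% (+6.0%) | +10.7% (+12.1%) |
| Vss | +1.7% (+2.1%) | +3.1% (+4.0%) |

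At 1% the uncorrected AUC shift is +5.3%, so the factor removes about a third of it (5.3 to 3.6).

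**Range.** Taking the pivotal half-life and IR ranges together, the T1/2 shift runs from +1.6% (52.34 h, IR 1.35, 1%, best fit) to +44% (15.83 h, IR 0.53, 2%, last three points). An assumed distribution phase (fraction 0.3-0.5, half-life 2-5 h) raises the median-half-life figure to roughly +8.5% to +25%.

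**Other rules in the SAP.** Requiring points above the pre-infusion level drops nothing in the one-phase model: the lowest adjusted 72 h value is 1.76 times the pre-infusion value. The below-1% rule leaves endogenous FIX of 0.9% uncorrected, with T1/2 +4.4% (last three: +5.7%).

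**Residual drug only.** Assuming an earlier 50 IU/kg, the residual is 50 x 0.87 x 2^(-120/24.58) = 1.5 IU/dL at 5 days and 0.4 at 7 days. With one-phase decay the SAP method then gives T1/2 0.0% and AUC within 0.1%. With the assumed distribution phase T1/2 is hardly affected, but AUC may be off by about 0.4% to 2% at the median half-life, and by about 3% to 5% (about 7% in the most extreme case tried) at 52.34 h after a 5-day washout.

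**The case against.** The strongest reply is about reach. These parameters come only from subjects who had an abbreviated PK study, SAP 5 records that all of them were adults, and no test or decision in the SAP uses the results. The number with endogenous FIX of 1-2% is not given and may be zero. This stands, and it is why the point is minor.

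Second, the separate PK specification was written for dosing recommendations, and the protocol sets the PK-tailored target relative to the subject's own baseline FIX. That document may well handle endogenous FIX. This also stands: the statement that no other rule removes the effect covers only the SAP text available. If the specification does handle it, SAP 9.2 should say so. The planned semi-logarithmic plots might reveal terminal curvature but would not correct it.

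Third, simple subtraction is not a safe replacement. A subject with no endogenous FIX can carry about 1.5 IU/dL residual drug after the minimum 5-day washout at both screening and PK. Subtracting that gives T1/2 of -7.4% (last three points -9.5%), where the SAP method gives 0.0%. This stands, and the proportional method should stay primary.

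A reader might infer that the primary and sensitivity half-lives enclose the true one. They need not. With assumed assay error (CV 5-10% plus 0.1-0.3 IU/dL) near the 1% limit and clean screening samples, they did so in only about 26% to 46% of simulated cases, although the sensitivity method's median bias stayed below 1%.

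**Conclusion.** The point holds, at minor severity. The claim that the adjustment keeps pre-infusion FIX out of the PK parameters is exact for one-phase residual drug, nearly so for T1/2 with a distribution phase, and wrong for constant endogenous FIX. That T1/2 and MRT are untouched by the factor is algebra and needs no model.

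The sizes do depend on a model. For a typical one-phase subject at 1% to 2% endogenous FIX, T1/2 is +5% to +10% (last three points +6% to +13%), MRT +5% to +11%, AUC +4% to +7% and CL -4% to -7%. These are not bounds: the T1/2 shift runs from about 2% to 44% over the pivotal half-life and IR ranges taken together.

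A reader might go further and infer that the trial's reported PK summaries are wrong by these amounts, or that dose recommendations were affected. The documents support neither. They do not give the number of PKFAS subjects with FIX of 1-2%, and the specification behind the dosing recommendations is not among them.

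**What to change.** In SAP 9.2:

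1. State that the factor assumes the pre-infusion value is residual drug, and that it does not alter T1/2 or MRT. Keep it as the primary method.
2. Report the number of PKFAS subjects whose screening FIX (parent-study screening for Cohort 1, this study's screening for Cohort 2) and PK pre-infusion FIX are both at least 1%.
3. If that number is not zero, give a sensitivity derivation of lambda_z, T1/2, AUC, MRT, CL and Vss for those subjects beside the primary result. Subtract the smaller of the two values from the pre-infusion value, Cmax and every post-infusion concentration, leave out concentrations not above it, and apply the existing factor to the remainder.
4. State the limits. The sensitivity result over-corrects if the screening value contains residual drug (T1/2 about -7% to -10% with 1.5 IU/dL in both samples). Endogenous FIX just below 1% is corrected by neither method. The two results are not to be presented as bracketing the true half-life.
5. If the separate PK specification already deals with endogenous FIX, cite the rule instead.

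The cost is SAP wording, one count and at most one NCA rerun, with no new samples. Cohort 1 needs the screening FIX value brought in from the parent study, because the data transcribed at entry come from that study's completion visit.
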